#### **Investigational Plan:**

**Screening:** Subjects who satisfy eligibility criteria and provide written informed consent may be entered into the study. The subject should have adequate, historical clinical data to provide a reasonable estimate of the rate of progression of CKD (re: Inclusion 7). Screening procedures include a full physical exam, ECG, and laboratory assessments (hematology, clinical chemistry, and urinalysis). An ultrasound will be performed to confirm the presence of two kidneys with normal anatomic features. A MRI study will determine kidney size and volume.

**Renal Biopsy:** Three days or less before undergoing renal biopsy, enrolled subjects will report to the clinic and undergo an interim physical exam along with an ECG and renal MRI (if not completed during or after the Screening Visit). Laboratory tests, including renal

function, hemoglobin, and a pregnancy test for females will also be performed. Eligible subjects satisfying all inclusions and exclusion criteria will be admitted to the hospital / clinical research center to undergo a kidney biopsy. A minimum of 2 tissue cores measuring at 1.5cm a piece must be collected using a 16-gauge biopsy needle to provide sufficient material for the manufacture of REACT. Subjects who do not experience complications from the biopsy may be discharged the same day consistent with site standard practice. Each individual subject's kidney biopsy tissue will be sent to ProKidney.

**REACT Injection:** Ten to 14 days before the scheduled injection date, subjects will undergo an interim physical exam for ongoing verification of inclusion and exclusion criteria. Subjects also will undergo renal scintigraphy (i.e., split kidney function scan) to find out what percentage each kidney contributes to total baseline kidney function. On the day of the scheduled REACT injection, eligible subjects will be admitted into the hospital / clinical research unit. After warming to liquefy the hydrogel, REACT will be injected into the same kidney that was previously biopsied using a percutaneous approach. This procedure will follow a standardized technique, such as that used in the ablation of renal masses by radiofrequency or cryogenic methods. Subjects without complications may be discharged the same day consistent with site standard practice. An ultrasound will be performed the day after injection to detect possible, subclinical AEs. It is anticipated that all subjects will receive 2 REACT injections given 6 months (+4 weeks) apart. The first and second injections will occur in the same kidney in which the biopsy was taken. Therefore, only one kidney will be used for the duration of this study.

**Follow-up:** Subjects will complete follow-up evaluations on Days 1, 7, 14, 28 ( $\pm$  3 days) and Months 2, 3, 4 and 5 ( $\pm$  7 days) after the first REACT injection, and on Days 1, 7, 14, 28 ( $\pm$  3 days) and Months 2 and 3 ( $\pm$  7 days) after the second REACT injection. Depending on when the second injection is administered (i.e., at 6 months [+4 weeks]), subjects may undergo evaluations at 6 months after the first REACT injection. Following the final REACT injection, subjects will complete long-term, follow-up assessments of safety and efficacy through 6, 9, 12, 15-, 18-, 21-, and 24-months post-treatment.

**Safety Monitoring:** Hemorrhage following REACT injection is a known and foreseeable risk to subjects participating in this study. Therefore, hemoglobin will be measured by the site's local laboratory at the following times: a) before, b) after procedure per site standard practice.

#### **Investigational Product, Dosage and Mode of Administration:**

**Investigational Product:** REACT is made from expanded autologous selected renal cells obtained from each individual subject's kidney biopsy. To manufacture REACT, biopsy tissue from each enrolled subject will be sent to ProKidney, in whose facilities renal cells will be expanded and SRC selected. SRC will be formulated in a gelatin-based hydrogel at a concentration of  $100 \times 10^6$  cells/mL, packaged in a 10 mL syringe, and shipped to the clinical site.

**Dosage:** The volume of REACT to be administered will be determined by pre-procedure MRI volumetric 3D evaluation or ellipsoid formula (Length x width AP plane x width Transverse plan x .62). Based on pre-clinical data, the dose of REACT will be  $3 \times 10^6$  cells/g estimated kidney weight (g KWest). Since the concentration of SRC per mL of REACT is  $100 \times 10^6$  cells/mL, the dosing volume will be 3.0 mL for each 100 g of kidney weight. Using this dosing paradigm, the following table shows the dosing volume and number of SRC to be delivered relative to estimated kidney weight. The maximum volume of REACT injected into the biopsied kidney will be 8.0 mL.

Estimated Kidney Weight (g KW est )*		Dosing Volume (mL)	SRC Delivered (Number of Cells x 10  )
Median Weight (g)	Weight Range (g)		
100	95 – 108	3.0	300
117	109 – 125	3.5	350
133	126 – 141	4.0	400
150	142 – 158	4.5	450
167	159 – 175	5.0	500
183	176 – 191	5.5	550
200	192 – 208	6.0	600
217	209 – 225	6.5	650
233	226 – 241	7.0	700
250	242 – 258	7.5	750
— — —	>259	8.0	800

\* Kidney weight will be estimated from the results of an MRI study performed on or after the Screening Visit until Day 0 (renal biopsy).

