**Table 9: Investigational Product**

	Investigational Product
Product Name:	Renal Autologous Cell Therapy (REACT)
Dosage Form:	Renal cells obtained from autologous kidney biopsy tissue will be expanded and SRC selected. SRC will be formulated in a gelatin-based hydrogel at a concentration of $100 \times 10^6$ cells/mL. This sterile cell preparation (REACT) will be contained in a sterile 10 mL syringe and shipped to the clinical site for use.
Unit Dose	The dose of REACT will be adjusted to $3 \times 10^6$ cells/g estimated kidney weight determined from MRI study.
Route of Administration	Percutaneous injection into the cortex of the biopsied kidney
Physical Description	Sterile, labelled, 10 mL syringe containing up to 8 mL of REACT
Manufacturer	ProKidney, Winston-Salem, North Carolina, USA

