### 3.2.5. REACT Dose

The dose of REACT for subjects in the Phase 1 clinical trials (TNG-CL010 and TNG-CL011) was  $3 \times 10^6$  SRC /g estimated kidney weight (g KWest). Similarly, in the present study, each REACT injection will contain  $3 \times 10^6$  cells/g KWest. Since the concentration of SRC is  $100 \times 10^6$  cells/mL of REACT, the dosing volume will be 3.0 mL for each 100 g of kidney weight. The volume of REACT to be administered will be determined by pre-procedure MRI volumetric 3D evaluation or

ellipsoid formula (Length x width AP plane x width Transverse plan x .62). Examples of dosing volumes based on estimated kidney weight are shown in Table 10.

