**Table 10: REACT Dosing Relative to Estimated Kidney Weight**

Estimated Kidney Weight (g KW est ) a,b		REACT Dosing Volume (mL)	SRC Delivered (Number of Cells x
Median Weight (g)	Weight Range (g)		
100	95 – 108	3.0	300
117	109 – 125	3.5	350
133	126 – 141	4.0	400
150	142 – 158	4.5	450
167	159 – 175	5.0	500
183	176 – 191	5.5	550
200	192 – 208	6.0	600
217	209 – 225	6.5	650
233	226 – 241	7.0	700
250	242 – 258	7.5	750
— — —	>259	8.0 c	800

Abbreviations: Estimated Kidney Weight (g KWest); SRC (Selected Renal Cells).

Notes:

a. The dose of REACT will be  $3 \times 10^6$  cells/g estimated kidney weight.

b. Kidney weight will be estimated from an MRI study performed before renal biopsy.

c. 8 mL will be the maximum dosing volume (mL).

The dose of REACT will be based on kidney volume calculated via MRI. In contrast to other methods, measurements of renal volume using MRI are more accurate, and acquire true tomographic data along any orientation without the risk of ionizing radiation or nephrotoxic contrast agents. Renal volume measurements (mL) estimated from MRI are approximately 92 to 97% of dry weight measurements in grams for isolated organs trimmed of perirenal fat. As a conservative approach, the REACT dose will be calculated using a conversion of one g equals one mL. The volume of REACT to be administered will be determined by pre-procedure MRI volumetric 3D evaluation or ellipsoid formula (Length x width AP plane x width Transverse plan x .62). This ensures that subjects will not receive REACT doses higher than those previously tested in animal studies.

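### Kidney weight, and so the dose, may come from MRI volumetry or from an ellipsoid formula with an unexplained factor of .62, and the two are not shown to agree

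*Protocol*

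**What the plan says.** The protocol states one dose per gram for everyone. Table 9: "The dose of REACT will be adjusted to $3 \times 10^6$ cells/g estimated kidney weight determined from MRI study". At 100 x 10^6 cells/mL this becomes, in the synopsis, "the dosing volume will be 3.0 mL for each 100 g of kidney weight", with a ceiling: "The maximum volume of REACT injected into the biopsied kidney will be 8.0 mL".

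Two routes to the kidney volume are allowed. The synopsis says the volume to be given is "determined by pre-procedure MRI volumetric 3D evaluation or ellipsoid formula (Length x width AP plane x width Transverse plan x .62", and section 3.2.5 repeats this before and after Table 10. None of the three places gives a source for the constant, says when each method is used, or says who decides.

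The text under Table 10 then argues that the conversion errs on the low side: "Renal volume measurements (mL) estimated from MRI are approximately 92 to 97% of dry weight measurements in grams for isolated organs trimmed of perirenal fat". It continues: "As a conservative approach, the REACT dose will be calculated using a conversion of one g equals one mL". The two methods are restated next and run straight into the assurance: "ellipsoid formula (Length x width AP plane x width Transverse plan x .62). This ensures that subjects will not receive REACT doses higher than" those already tested in animals.

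Section 3.2.5.2 describes the repeat-dose canine study as having used twice the clinical dose.

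On recording, protocol section 7.4.3 has the MRI process defined site by site and imaging parameters entered in the CRF. It does not name the volume method as an item. The SAP summarises total volume injected (7.1) and screening kidney volume (5.3), but not cells per gram or the volume method.

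**The concern.** The volume of an ellipsoid is pi/6 times the product of its three axes. The constant .62 is larger than pi/6, so the formula does not return the volume of the shape it names. If the two methods differ systematically, subjects with the same kidney receive different volumes and cell numbers under a plan that describes a single dose per gram.

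Three things depend on this. The low-side argument under Table 10 rests on a 3-8% margin, which a larger constant could use up. The animal margin in section 3.2.5.2 is stated per gram. And with up to 10 subjects at up to 10 centres, and the MRI process set by site, method could be confounded with site without the planned outputs showing it.

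**Working it through.** **1. The plan's own table.** Volume = median weight x 3/100. The ten medians in Table 10 give 3.00, 3.51, 3.99, 4.50, 5.01, 5.49, 6.00, 6.51, 6.99 and 7.50 mL. These match the tabulated 3.0 to 7.5 mL after rounding, so the table is sound once a weight is given.

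**2. The constant.** An ellipsoid with full axes L, W and D has volume 4/3 x pi x (L/2)(W/2)(D/2) = (pi/6) x L x W x D, and pi/6 = 0.5236. Then 0.62/0.5236 = 1.184, which is 18.4% more. This is geometry and is not stated in the documents.

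**3. Could .62 convert straight to grams?** With the protocol's ratio of 92-97%, such a factor would be 0.5236/0.97 = 0.540 to 0.5236/0.92 = 0.569. Neither reaches .62.

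**4. Through the dosing table.** Assumptions: a truly ellipsoidal kidney, accurate volumetry, 1 mL = 1 g as the protocol directs, weights rounded to 1 g, and the top row applied from 259 g.

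| Volumetry (mL) | x 1.184 | Volume by volumetry (mL) | Volume by .62 formula (mL) | Gap |
|---|---|---|---|---|
| 100 | 118.4 | 3.0 | 3.5 | 17% |
| 150 | 177.6 | 4.5 | 5.5 | 22% |
| 200 | 236.8 | 6.0 | 7.0 | 17% |
| 250 | 296.0 | 7.5 | 8.0 (cap) | 7% |
| 259 | 306.7 | 8.0 | 8.0 (cap) | 0% |

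Every listed median moves up one or two rows. For each whole mL from 95 to 218, the gap is 0.5-1.5 mL, or 9-33%, with a mean of 18%. From 259 mL it is zero. Below the table, a 92 mL kidney has no row by volumetry but reads 92 x 1.184 = 109 g by the formula, which is the 3.5 mL row.

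**5. Cells per true gram, before table rounding and below the cap, using the 92-97% ratio.**
- Volumetry: 3.0 x 0.92 = 2.76 to 3.0 x 0.97 = 2.91 x 10^6.
- .62 formula: 3.0 x 1.184 x 0.92 = 3.27 to 3.0 x 1.184 x 0.97 = 3.45 x 10^6, which is 9-15% above the nominal 3.0.

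**6. Against the animal doses.** The highest value found with the .62 formula and table steps, taking 1 mL = 1 g, is 350/92 = 3.8 x 10^6 cells/g. Table 5 gives 660/120 = 5.5 x 10^6 cells/g per dose in the repeat-dose canine study. The rat NOAEL is 6.25 (section 1.4.1).

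**7. The two-fold statement.** Against the nominal dose, 5.5/3.0 = 1.83 whatever the volume method. Per true gram as in step 5, the formula gives 5.5/3.45 = 1.60 to 5.5/3.27 = 1.68, and volumetry gives 5.5/2.91 = 1.89 to 5.5/2.76 = 1.99.

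**The case against.** The strongest reply is that kidneys are not ellipsoids. What matters is whether length x width x width x .62 agrees with MRI volumetry in real kidneys, and the documents hold no data either way. If .62 was fitted to kidneys, the methods may agree on average and the 18.4% disappears. This stands, and it limits the point to an unexplained constant and two methods not shown to be interchangeable. A reader might infer that subjects dosed by the formula receive 18% too much. The documents do not support that: they show neither that the formula overestimates real kidneys nor that any site used it.

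A reader might also infer that the whole safety argument under Table 10 fails. It does not. Its stated purpose is to stay within doses tested in animals, and about 3.8 is well below 5.5 x 10^6 cells/g. Injected volume is also within tested limits per gram: 3.8 x 10^6 cells/g is 0.038 mL/g, against 0.083 mL/g reported as well tolerated in dogs (section 1.3.2.3). Only the understatement of weight is lost, and only for one method.

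Nor is 18% the delivered difference: the 0.5 mL steps and the 8.0 mL cap change it at every size. The two-fold wording is a separate matter. At 1.83 it is loose rounding that does not come from .62. Finally, section 7.4.3 already puts imaging parameters in the CRF, so recording may be partly covered.

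**Conclusion.** The point holds as a defect of specification. A constant that sets the dose does not match the shape it is named after. Two methods are allowed with no selection rule and no evidence of agreement, and the text that calls the conversion conservative covers both although its reasoning fits one.

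For an ellipsoidal kidney measured accurately by volumetry, the formula gives 18.4% more estimated weight, with the stepped and capped differences in delivered volume shown above. The geometry is certain. The size in real kidneys is unknown, because it rests on the ellipsoid assumption. No tested animal dose is exceeded under any case computed here.

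The canine margin is 1.83-fold against the nominal dose, and about 1.6-1.7-fold per true gram under the formula on the same assumptions, where section 3.2.5.2 says two-fold.

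**What to change.** Reconcile the synopsis dosage text, section 3.2.5 (including the text under Table 10) and section 3.2.5.2. The choice of method, constant and dose is the sponsor's.

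- State where .62 comes from and how it agrees with MRI volumetry, or align it with the ellipsoid named.
- State which method applies when.
- Limit the conservative wording to the method for which it holds.
- Restate the canine margin to match Table 5.
- Record the volume method and estimated kidney weight for each subject, including those already dosed, so that delivered cells per gram can be reported on one common basis.

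The cost is a protocol clarification and a small CRF addition. The MRI is already scheduled, so no new procedure is needed. The stated animal margin becomes slightly less favourable.

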**Investigational Product, Dosage and Mode of Administration: Dosage (continued)**

It is anticipated that all subjects will receive two planned REACT injections to allow dose-finding and evaluate the duration of effects. The first and second injections will occur in the same kidney in which the biopsy was taken. In some cases, a subject or the Investigator may decide to postpone or withhold the second REACT injection. For example, if there appears to be any untoward safety risk, or rapid deterioration of renal function, or the development of uncontrolled diabetes or uncontrolled hypertension, or the development of a malignancy or an intercurrent infection, then the second REACT injection should not be administered.

**Mode of Administration:** REACT will be injected into the biopsied kidney using a percutaneous approach. The percutaneous method will employ a standardized technique (such as that utilized in the ablation of renal masses by radiofrequency or cryogenic methods).

**Data Safety Monitoring Board:** A Data Safety Monitoring Board (DSMB) will be chartered to oversee subject safety, especially as it relates to unexpected investigational product-related events. The DSMB will minimally consist of 3 members who have expertise directly related to protocol-specified activities. It will function independently, and its members will have no other engagement with ProKidney. The DSMB will meet by teleconference at regular intervals, depending on the speed of subject enrollment and the amount of new data generated. The DSMB will advise ProKidney on aspects concerning the safety of subjects participating in the clinical trial. Apart from reviewing study data, the DSMB will consider feedback from the Sponsor and Investigators. The DSMB will share its recommendations with the study centers, Institutional Review Boards/Ethics Committees, and regulatory authorities, as appropriate. Other specific activities and responsibilities of the DSMB will be detailed in the DSMB charter.

**Statistical Analysis Methods:** Statistical analyses will be primarily descriptive in nature and no statistical hypothesis testing is planned for the study. Unless otherwise specified, continuous variables will be summarized by presenting the number of non-missing observations (n), mean, standard deviation, median, minimum, and maximum. Categorical variables will be summarized by presenting frequency count and percentage for each category.

**Table 1: Time and Events Table**

Abbreviations: AE (adverse event); ConMeds (concomitant medications); DSMB (Data Safety and Monitoring Board); ECG (electrocardiogram); EOS (End-of-Study Visit); I /E (inclusion /exclusion); KDQOL (Kidney Disease Quality of Life Survey); MRI (magnetic resonance imaging); REACT (Renal Autologous Cell Therapy); PE (physical examination).

Notes:

- \* Day 1 follow-up visit should only be conducted if there is a safety event identified during or after the kidney biopsy.
- \*\* Every attempt should be made to ensure the second REACT injection is administered 6 months (+4 weeks) after the first injection. In the event that the subject cannot schedule his/her second REACT injection 6 months after receiving the first injection or cannot keep his/her scheduled 6-month visit, ProKidney and the Medical Monitor must be notified immediately. The expectation is that the subject and the clinical center will accommodate the Sponsor's preference that the series of 2 REACT injections should be administered no more than 6 months apart.
- a. If the screening assessment falls outside of the 60-day window before renal biopsy, re-screening will be performed as described in Screening ([Section 6.1](#)).
- b. Because the second REACT injection will occur 6 months (+4 weeks) after the first injection, the 6-month visit may not be scheduled.
- c. In the event that a second REACT injection will not be administered, the subject will undergo all follow-up assessments after the last REACT injection at the 24-month EOS Visit.
- d. The EOS Visit will take place 24 months after the last REACT injection, or when the subject is terminated from the study by the Investigator ([Section 8.6](#)) or when the subject voluntarily discontinues from the study ([Section 5.4](#)).
- e. The Informed Consent Form must be signed and dated prior to conducting any study-specific procedures, including those at the Screening Visit. Signing the Informed Consent Form starts the 60-day timeline for screening.
- f. The PE and interim PE are described in [Section 7.2.2](#).
- g. Vital signs include heart rate, resting blood pressure, respiration rate, and body temperature. ([Section 7.2.1](#)). At the Pre-Biopsy Visit (Day -3 to Day -1) and the Pre-Injection Visit (Day -14 to Day -10) three BP measurements will be taken and the average will be used to satisfy entry criteria.
- h. Vital signs (included are heart rate, blood pressure, and respiration rate) will be measured throughout the procedure. Temperature is not required to be recorded throughout the procedure.
- i. Refer to [Table 2](#) for a schedule of laboratory assessments.
- j. Ultrasound will be performed at the Screening Visit to verify subject eligibility and to obtain baseline echogenicity reading. Subsequent Ultrasounds will monitor echogenicity.
- k. Ultrasound will be performed following the in-patient renal biopsy on Day 0 and Day 1, and following the in-patient REACT injection(s) on Day 0 and Day 1 with the aim of monitoring possible, subclinical AEs.
- l. A MRI study without contrast will be performed at the Screening Visit through Day -1 before renal biopsy to determine kidney size and volume.
- m. Renal scintigraphy will be performed before the first REACT injection, before the last REACT injection, at the 6-Month Visit after the last REACT injection, at the 12-Month Visit after the last REACT injection, and at the month 24/EOS Visit.
- n. The REACT preparation will be handled and injected according to procedures described in the Study Reference Manual.
- o. CT Scan must be used in conjunction with ultrasound for the REACT injection procedure.
- p. Subjects may be admitted to hospital per site standard practice. Subjects who do not experience complications may be discharged the same day consistent with site standard practice.
- q. Subjects will undergo a funduscopic exam with retinal photography of both retinae to monitor diabetic retinopathy at screening, month 12, and month 24/EOS visit.

**Table 2: Laboratory Time and Events Table**

Laboratory Evaluation:	Screening Visit		Optionala
	Day -60 to -3 a	Day -3 to -1	
	Day -3 to -1	Renal Biopsy	
	Day 0 Biopsy	Day 1 Follow-up	
Clinical Chemistry			
Standard panel	X	X	X
Renal analytes	X	X	X
Lipid panel	X		
Pregnancy test e	X	X	
FSH test f	X		
Serology			
HIV, HBV, HCV	X		
Hematology			
Standard cell counts/indices	X	X	X
Hemoglobin, Hematocrit g		X h	
Coagulation Status			
Platelet count	X	X	
APTT	X	X	
PT-INR	X	X	
Urine Collection			
Standard panel (Micro and Macro)	X	X	X
Urine Chemistry		X	X
24-hour	X		
Test stick (Spot Urine)		X i	X i
Additional Tests			
HbA 1c	X		
Drugs of abuse	X		
iPTH	X	X	
β2-microglobulin j	X	X	
NGAL	X	X	
Research (reserve) samples k	X	X	

Preparation and Shipment of REACT Product	Day -14 to -10	First REACT Injection	Optionalb
	Day 0 REACT Injection	Day 1 Follow-up	
	Day 14 (± 3 days)	Follow-up First REACT Injection	
	Day 28 (± 3 days)	Months 2, 3, 4, and 5 (± 7 days)	
	Month 6 (± 7 days)	Month 6 (± 7 days)	
	Day -14 to -10	Last REACT Injection	
	Day 0 REACT Injection	Day 1 Follow-up	
	Day 14 (± 3 days)	Follow-up Last REACT Injection	
	Day 28 (± 3 days)	Month 2 Month 3 (± 7 days)	
	Month 6, 9, 12, 15, 18, 21 (± 7 days)	Month 24 (± 7 days)	EOS d

Interval Between REACT Injections = 6 Months (+) 4 Weeks**	Day -14 to -10	First REACT Injection	Optionalb
	Day 0 REACT Injection	Day 1 Follow-up	
	Day 14 (± 3 days)	Follow-up Last REACT Injection	
	Day 28 (± 3 days)	Month 2 Month 3 (± 7 days)	
	Month 6, 9, 12, 15, 18, 21 (± 7 days)	Month 24 (± 7 days)	EOS d
	Day -14 to -10	Last REACT Injection	
	Day 0 REACT Injection	Day 1 Follow-up	
	Day 14 (± 3 days)	Follow-up Last REACT Injection	
	Day 28 (± 3 days)	Month 2 Month 3 (± 7 days)	
	Month 6, 9, 12, 15, 18, 21 (± 7 days)	Month 24 (± 7 days)	EOS d

Abbreviations: APTT (Activated Partial Thromboplastin Time); FSH (Follicle Stimulating Hormone; HbA1c (glycosylated hemoglobin); HIV (Human Immunodeficiency Virus); HBV (Hepatitis B Virus); HCV (Hepatitis C Virus); NGAL (Neutrophil Gelatinase-Associated Lipocalin); REACT (Renal Autologous Cell Therapy); i PTH (Parathyroid Hormone, intact); PT-INR (Prothrombin Time-International Normalized Ratio)

Notes:

- \* Day 1 follow-up visit should only be conducted if there is a safety event identified during or after the kidney biopsy.
- \*\* Every attempt should be made to ensure the second REACT injection is administered 6 months (+ 4 weeks) after the first injection. In the event that the subject cannot schedule his/her second REACT injection 6 months after receiving the first injection, or cannot keep his/her scheduled 6-month visit, ProKidney and the Medical Monitor must be notified immediately. The expectation is that the subject and the clinical center will accommodate the Sponsor's preference that the series of 2 REACT injections should be administered no more than 6 months apart.
  - a. If the screening assessment falls outside of the 60-day window before renal biopsy, re-screening will be performed as described in Screening ([Section 6.1](#)).
  - b. Because the second REACT injection will occur 6 months (+4 weeks) after the first injection, the 6-month visit may not be scheduled.
  - c. In the event that a second REACT injection will not be administered, the subject will undergo all follow-up assessments after the last REACT injection at the 24-month EOS Visit.
  - d. The EOS Visit will take place 24 months after the last REACT injection, or when the subject is terminated from the study by the Investigator ([Section 8.6](#)), or when the subject voluntarily discontinues from the study ([Section 5.4](#)).
  - e. The clinic will perform a urine dip-strip pregnancy test. If positive, then a confirmatory test will be performed by the central laboratory.
  - f. Post-menopausal women with a confirmatory FSH test do not have to undergo pregnancy testing throughout the study.
  - g. Within 48 hours before Days 0 for renal biopsy and REACT injection(s), hemoglobin levels will be verified as > 9 g/dL per site standard practices.
  - h. On Days 0 for renal biopsy and REACT treatment (s), hemoglobin and hematocrit will be measured before and after procedure per site standard practice at the local lab. These samples will be processed by the site's local laboratory to accelerate notification of results and subsequent decisions affecting clinical care. Additionally, blood samples for hemoglobin and hematocrit after procedure will be sent to the central laboratory where results can be entered into the study database.
  - i. Prior to, day of, and day after biopsy and REACT injection(s), microscopic urinalysis will be performed using a dip (test) stick
  - j.  $\beta$ 2-microglobulin will be assessed in both serum and urine samples.
  - k. Research samples (serum/plasma and urine) will be collected, frozen, and stored for the evaluation of novel biomarkers.

